Biochemistry (including CRP) / Haematology, ESR	X	X	X	X	X	X	X	X	X	X	X	X	X	
Immunology tests  : ANA (including dsDNA) anti-CCP and RF	X										X	X	X	
Blood and urine collection for biomarkers (Biological Sub-study)		X			X			X		X	X	X	X	
Urinalysis 	X													
Pregnancy test 	X													
Whole-Body MRI (WB-MRI) 	X							X		X		X 	X 	

Study Period	Period 1: Double-blind randomised									Period 2: Observational*				Withdrawal visit **
	Screen	Baseline	(Safety)	(Safety)	Secondary outcome	(Safety)	(Safety)	Primary outcome	(Safety)	Secondary outcome	End of study visit	Extra Visit		
Study Phase														
Week	-4 to 0	0	4 (±7 days)	8 (±7 days)	12 (±7 days)	16 (±7 days)	20 (±7 days)	24 (±7 days)	28 (±7 days)	36 (±7 days)	52 (±7 days)	Y***	X	
Visit number	1	2	3	4	5	6	7	8	9	10	11	98	99	
Musculoskeletal US scan 	X				X			X		X		X 	X 	
Chest-X-ray  , ECG	X													
Plain X-ray of Hands and Feet 	X													
X-ray of the orbits 	X													
Physician VAS global disease Activity	X	X			X			X		X	X	X	X	
Physician Likaert scale, articular disease Activity	X	X		X	X			X		X	X	X	X	
Patient VAS global disease Activity	X	X			X			X		X	X	X	X	
Patient VAS articular pain	X	X			X			X		X	X	X	X	
Patient Likaert scale, articular disease Activity	X	X		X	X			X		X	X	X	X	
HAQ	X	X			X			X		X	X	X	X	
DLQI	X				X			X		X	X	X	X	
SF-36	X	X			X			X		X	X	X	X	
ASQoL	X				X			X		X	X	X	X	
BASDAI		X			X			X		X	X	X	X	
Administration of SC IMP 		X	X	X	X	X	X	X						

**1.** At screening visit; end of study visit (visit 11, week 52); extra visit (week Y); and withdrawal visit (week X), immunology tests should not be repeated if results available within 20 days prior to study visit.

If subjects do not have a chest x-ray or hands/feet x-ray performed within 3 months of screening, an x-ray should be performed after it is certain the subject meets the inclusion/exclusion criteria (in order to minimize exposure to x-ray radiation).

X-ray of the orbits should be performed only in subjects contraindicated to WB-MRI, who report a personal history suggestive of metallic fragments present in the orbits.

**2, 3.** Urinalysis and Pregnancy test can be repeated in other visits as clinically indicated.

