## 8.7 Screening visit

The screening period should not last longer than four weeks. The aim of the screening visit is to identify a patient who might be suitable for inclusion in the study. The following will be performed either at this visit (or during the permitted 4 week screening period) and recorded in the eCRF:

- Full informed consent.

*The patient will have received information, including the Patient Information Sheet, at least 24 hours before the screening visit. Their knowledge of the nature and objectives of the study will be verified and his/her informed consent will be obtained. The screening period will provide further opportunity for a patient to re-consider and consent will be confirmed at the baseline visit.*

- Inclusion/exclusion criteria available at this time will be recorded.
- Demographic variables describing the patient (age, sex, and ethnic group), smoking and alcohol intake history
- Medical and surgical history, family history, PsA-related history will be recorded.
- Concomitant medications.
- Duration of articular morning stiffness.
- PsA-related comorbidities.
- Physical examination.
- Measurement of body weight and height; body mass index.
- Vital signs (blood pressure after a 5-minute rest, pulse rate and body temperature).
- 12-lead ECG.
- Articular examination (76 swollen and 78 tender joint counts and grading).
- Laboratory tests:
  - Haematology, blood chemistry.
  - CRP and ESR.
  - Immunology tests (ANA, anti-dsDNA, anti-CCP, RF - (unless already performed within 20 days prior to screening visit)
  - Infectious hepatitis screen (Hep B surface antigen, Hep B core antibody, anti-HCV antibody).
  - QuantiFERON test for TB testing.
  - HIV testing
  - Urinary tests:
    - Pregnancy test in female patients with child-bearing potential (see [appendix 1](#)).
    - Urinalysis (dipstick for blood, protein and nitrites).

- Patient-reported outcomes (disease activity and pain VAS, assessment of articular disease on Likaert scale, HAQ, SF-36)
- Physician VAS assessment of global disease activity and assessment of articular disease on Likaert scale.
- LEI and LDI
- MRI eligibility checklist (only to be conducted during WB-MRI subset recruitment period)
- WB-MRI (if in WB-MRI subset; to be performed between screening visit and week 0)
- US (to be performed between screening visit and week 0)
- Radiographs of chest, hands and feet (unless performed within 3 months of screening).

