#### 11.5.3. Other analyses

A number of sensitivity analyses will be conducted. These will include restricting analysis of the data to the observed values only, imputing non-response for patients who withdraw for any reason, using post-withdrawal data observed for patients who withdrew from study therapy early rather than carrying forward data from their withdrawal visit, and amending imputed values for continuous variables to investigate the robustness of response estimates to a variety of deviations from the missing at random assumption. A per protocol analysis will also be performed, repeating the primary endpoint analysis in the PPS. Further details of these sensitivity analyses will be set out in the statistical analysis plan.

In a subset of patients, total synovitis and enthesitis scores calculated in expanded sets of joints defined in the newly published OMERACT definitions will be compared between groups according to the same methods as for secondary outcomes. In addition, for patients in the WB-MRI subset the MRI outcomes will be compared between groups on an exploratory basis using the same methods as for secondary outcomes. However, the focus will be on quantifying the potential treatment effect. A range of confidence intervals (75%, 85%, 95%) around the difference between the treatment arms will be calculated, to indicate the level of confidence with which we could say there was potential for a substantive difference between groups.

An assessment of the test-retest reliability of the PASDAS will be performed, by calculating the intraclass correlation coefficient between PASDAS measurements collected at screening and baseline with a 95% confidence interval.

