## **11.9 Determination of sample size and randomization method**

Using in-house unpublished data we estimated the minimum clinically important difference to be 0.7 units on the PASDAS; this is similar to a published value for smallest detectable difference of 0.8 units (11). We will aim to detect a difference of at least 1 unit between the treatment arms in this study. The standard deviation of PASDAS in the TICOPA MTX rapid escalation arm (56, 57) at 24 weeks (restricted to patients who remained on methotrexate throughout) was 1.57. Assuming  $\delta=1$ ,  $\sigma=1.57$ , at alpha=0.05 and 1-Beta=0.8 this would require 78 patients. Originally the sample size for the trial was adjusted to account for 10% drop-out, requiring a total of 88 (44 per group). However, because recruitment had been slower than anticipated, in part due to the SARS-CoV-2 pandemic, drop-out was reassessed once 76 participants had the opportunity to reach the primary endpoint. Only 4 (5%) had withdrawn from follow-up prior to that point. Therefore, the total required sample size was revised down to 84 (42 per group) i.e. allowing for 5% drop-out.

For the whole-body MRI subset, published rules of thumb for pilot studies indicate that between 12 and 30 patients per group should be included. We will aim to continue recruiting patients into the WB-MRI subset until there are at least 30 patients (15 per group) with scans available at both baseline and week 24, at which point WB-MRI will cease to be performed in the remaining patients.

To estimate the ICC between two repeated readings of the PASDAS composite index with a confidence interval of width 0.2, we would need 31 patients assuming the ICC is 0.85. For the patient's global assessment of disease activity VAS, which provides the greatest loading on the PASDAS score, ICC = 0.87(35). We will aim to obtain data from at least 31 patients.

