6. SAMPLE SIZE DETERMINATION

Using in-house unpublished data we estimated the minimum clinically important difference to be 0.7 units on the PASDAS; this is similar to a published value for smallest detectable difference of 0.8 units^[13]. We will aim to detect a difference of at least 1 unit between the treatment arms in this study. The standard deviation of PASDAS in the TICOPA MTX rapid escalation arm^[14,15] at 24 weeks (restricted to patients who remained on methotrexate throughout) was 1.57. Assuming $\delta=1$, $\sigma=1.57$, at $\alpha=0.05$ and $1-\beta=0.8$ this would require 78 patients. Originally the sample size for the trial was adjusted to account for 10% drop-out, requiring a total of 88 (44 per group). However, because recruitment had been slower than anticipated, in part due to the SARS-CoV-2 pandemic, drop-out was reassessed once 76 participants had the opportunity to reach the primary endpoint. Only 4 (5%) had withdrawn from follow-up prior to that point. Therefore, the total required sample size was revised down to 84 (42 per group) i.e. allowing for 5% drop-out.

For the whole-body MRI subset, published rules of thumb for pilot studies indicate that between 12 and 30 patients per group should be included. We will aim to continue recruiting patients into the WBMRI subset until there are at least 30 patients (15 per group) with scans available at both baseline and week 24, at which point WB-MRI will cease to be performed in the remaining patients.

To estimate the ICC between two repeated readings of the PASDAS composite index with a confidence interval of width 0.2, we would need 31 patients assuming the ICC is 0.85. For the patient's global assessment of disease activity VAS, which provides the greatest loading on the PASDAS score, $ICC = 0.87^{[1]}$. This element was added in an amendment and will not be available for all patients; we will aim to obtain data from at least 31 patients.

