8.2 Methods for Withdrawals, Missing Data, and Outliers

For missing values at baseline, screening values (if available) will be carried forward.

Visits which fall outside ± 14 days of the scheduled date will be considered missing for analysis.

For patients who withdraw early, in the primary analysis data from the withdrawal visit will be imputed for subsequent visits for continuous outcomes, and non-response will be imputed for binary outcomes.

Multiple imputation by chained equations will be used to address the remainder of the missing data for primary and secondary outcomes. The number of imputed datasets will be determined by the Monte Carlo (MC) error rate of the resulting combined estimates. A minimum of 20 datasets will be imputed; if the MC errors calculated for the coefficient and standard error for the treatment group term are more than 10% of the estimated standard error the number of imputations will be increased in increments of 5 until the MC error is <10% of the standard error. Continuous interval, count or ordinal outcomes will be imputed using predictive mean matching to 10 nearest neighbours; categorical outcomes will be imputed using binary, ordinal or multinomial logistic regression as appropriate to the data type. Composite measures, including the primary outcome, and the achievement of thresholds of response (e.g. PsARC) will be computed passively following imputation of the underlying score or components, provided sample size is sufficient for the imputation models to converge. If the number of parameters to be estimated exceeds the number of patients, these variables will be directly imputed.

All imputation models will include:

Age at baseline, sex, oligo/polyarticular disease, treatment arm, symptom duration at baseline, baseline values of the variables being imputed (values of components for response variables), other auxiliary variables found to be associated with the outcome to be imputed and/or with the likelihood that it is missing. Only values from the main primary and secondary endpoints (12, 24, 36, 52 weeks) will be included in imputation models. If imputation models continue to fail, mixed modelling will be explored as an alternative – see section 11.2 for details.

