11.3 Other Efficacy Variable Analyses

A number of sensitivity analyses will be conducted. In addition to sensitivity analyses relating to missing data or outliers (see section 8.2) and stratification status (see section 11.1), a per protocol analysis will be performed, repeating the primary endpoint analysis in the Per Protocol Set. In addition, comparisons will be made between PsARC response status calculated using the 68/66 tender/swollen counts originally specified by the criteria and response status calculated using the extended 78/76 joint counts. McNemar's tests will be used to compare response status according to the reduced and expanded joint counts. This will be performed in the observed data (i.e. without imputation).

See section 8.6 for details of planned exploratory analysis of baseline predictors of response to treatment.

In a subset of patients, total synovitis and enthesitis scores calculated in expanded sets of joints defined in the newly published OMERACT definitions will be compared between groups according to the same methods as for secondary outcomes. This will be conducted in the subset of participants with for whom the expanded joint scores were collected at screening. In addition, for patients in the WB-MRI subset the WB-MRI lesion scores will be compared between groups on an exploratory basis using the same methods as for secondary outcomes. However, the focus will be on quantifying the potential treatment effect. A range of confidence intervals (75%, 85%, 95%) around the difference between the treatment arms will be calculated, to indicate the level of confidence with which we could say there was potential for a substantive difference between groups. The biomarker sub-study data (available in a subset of patients) are to be analysed separately as part of a number of collaborative projects with other centres. Analysis plans for these projects will be produced separately.

An assessment of the test-retest reliability of the PASDAS will be performed, by calculating the intraclass correlation coefficient ($ICC_{(1,1)}$) between PASDAS measurements collected at screening and baseline; a 95% confidence interval will be constructed.

If sufficient patients in each group receive additional steroid injections at week 8, g-methods will be used to investigate the extent to which this is associated with total PDUS (US GLOESS) score at week 12.

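### The PASDAS test-retest ICC has no check that disease was stable between screening and baseline, so any true change over up to four weeks is counted as measurement error

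*SAP*

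**What the plan says.** Protocol 2.3 and SAP 3.1.2 list test-retest reliability of PASDAS as a secondary objective. Protocol 11.5.3 plans the "intraclass correlation coefficient between PASDAS measurements collected at screening and baseline with a 95% confidence interval". SAP 11.3 names the form, ICC(1,1), taken "between PASDAS measurements collected at screening and baseline; a 95% confidence interval will be constructed".

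On timing, Protocol 8.7 states: "The screening period should not last longer than four weeks". That is a ceiling; no minimum or target retest interval is given.

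On numbers, SAP 6 plans the ICC "with a confidence interval of width 0.2, we would need 31 patients assuming the ICC is 0.85", and adds: "This element was added in an amendment and will not be available for all patients".

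SAP 8.2 has a general rule that bears on the pairs: "For missing values at baseline, screening values (if available) will be carried forward". It does not exempt the reliability analysis.

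Neither document sets a stability criterion, an external anchor or a sensitivity analysis for this ICC. The schedule in Protocol 8.6 does collect possible anchors at both visits: "Physician Likaert scale, articular disease Activity" and the matching patient scale. Neither is a component of the PASDAS formula in Protocol 8.1.

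**The concern.** A test-retest coefficient measures the instrument only if the thing measured stays still between readings. ICC(1,1) has one within-patient term, so random error, true individual change and a mean shift between visits all go into it. The patients have active, DMARD-naive disease, and Protocol 1.1 describes the course of PsA as variable. The patient global VAS in Appendix 6 asks about the preceding week, so readings several weeks apart refer to different weeks.

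The stake is interpretation. If the ICC came out clearly below the planning value of 0.85, a reader could not tell whether PASDAS is unreliable or the patients changed. This concerns the instrument that carries the primary endpoint.

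**Working it through.** **1. The plan's own figure.** Inputs from SAP 6: ICC r = 0.85, full interval width w = 0.2, k = 2 readings, 95% confidence. Bonett's formula:

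n = 8z²(1−r)²[1+(k−1)r]² / [k(k−1)w²] + 1 = 8 × 3.8415 × 0.15² × 1.85² / (2 × 0.04) + 1 = 30.58, rounded up to 31.

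The stated 31 reproduces and is not in dispute. As a cross-check, the F-based interval at n = 31 and ICC 0.85 is 0.714 to 0.924, a width of 0.21.

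**2. Effect of true change.** The documents give no SD for change between screening and baseline, and no baseline SD for PASDAS. Both are assumed here:
- S is the single-visit SD. The only SD in the documents is 1.57 (SAP 6), a week-24 value from another trial. S = 1.0 is shown as an alternative.
- d is the SD of true within-patient change, from 0 to 1.0.
- The error-only ICC is taken as 0.85, the planning value.

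Two ways of adding change bracket the model choice:
- (A) Independent change added at the second visit: ICC = 0.85S² / (S² + d²/2).
- (B) Single-visit variance held fixed: ICC = 0.85 − d²/(2S²).

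Example for (A), S = 1.57, d = 0.5: 0.85 × 2.4649 / (2.4649 + 0.125) = 2.0952 / 2.5899 = 0.809.

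| d | S = 1.57, (A) | S = 1.57, (B) | S = 1.0, (A) | S = 1.0, (B) |
|---|---|---|---|---|
| 0 | 0.850 | 0.850 | 0.850 | 0.850 |
| 0.3 | 0.835 | 0.832 | 0.813 | 0.805 |
| 0.5 | 0.809 | 0.799 | 0.756 | 0.725 |
| 0.7 | 0.773 | 0.751 | 0.683 | 0.605 |
| 1.0 | 0.707 | 0.647 | 0.567 | 0.350 |

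A mean shift m = 0.3 with no individual variation, at S = 1.57, gives (0.85S² − m²/4) / (S² + m²/4) = 2.0727 / 2.4874 = 0.833.

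**3. Effect on precision.** Under (B) with S = 1.57 and d = 0.5, the Bonett width at n = 31 rises from 0.20 to 0.26, and 52 patients would be needed to hold 0.2.

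**4. A bias in the other direction.** If the SAP 8.2 carry-forward rule reached this analysis, a fraction q of pairs would be identical. The ICC becomes 1 − (1−q) × (within-patient share of variance). With q = 10% (assumed), 0.85 becomes 1 − 0.9 × 0.15 = 0.865, and the (B) value for d = 0.5, S = 1.57 rises from 0.799 to 0.819.

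**5. What a stable subset would do.** If 16 of 31 patients qualified (assumed), the Bonett width at ICC 0.85 would be about 0.28. Selection can also inflate the result. Suppose there is no true change, 60% of patients are kept, and the Likert change is normal with correlation ρ to the PASDAS difference. Keeping the middle 60% cuts the variance of the Likert change to 0.215 of its value, so within-patient PASDAS variance is multiplied by f = 1 − 0.785ρ². Then ICC = (1.85 − 0.15f) / (1.85 + 0.15f). For ρ = 0.5, f = 0.804 and the ICC is 0.878. For ρ = 0.7, f = 0.615 and the ICC is 0.905. The true value in both cases is 0.85.

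**The case against.** The strongest case against is that the plan limits change more than it first appears, and that the size of any bias is conjecture.

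- Four weeks is a maximum, and Protocol 6.6.3 and SAP 4.3 call for randomisation promptly after consent, which is taken at screening.
- Trial drug, methotrexate and the steroid bolus begin only at baseline.
- EXCL17 bars recent systemic or intra-articular steroids before screening. Protocol 7.3 and 7.6.2 bar oral steroids until week 24 without giving a start date, so they can be read as covering the gap. Protocol 7.6.2 also asks for steady NSAID doses during the study.
- The same assessor is preferred across visits (Protocol 8.2 and 8.7).

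All of this stands. It makes large changes less likely, but none of it tests whether disease activity was stable.

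Three stronger readings are tempting, and the documents support none of them. A reader might infer that every randomised patient enters the ICC; SAP 6 says the data exist only for some. A reader might infer that reliability will be understated by a material amount. That depends on an unmeasured quantity: at d = 0.3 and S = 1.57 the loss is under 0.02, and if disease was stable there is none. Taking d = 0.7, the plan's minimum important difference, as an SD of change would mean, under normality, that about 32% of patients truly move by more than 0.7 before any trial treatment. Nothing in the documents says so. Third, a reader might conclude that the Likert-stable subset should carry the conclusion. Those ratings cover articular disease only, whereas PASDAS also includes enthesitis, dactylitis, CRP, SF-36 PCS and a patient global spanning skin and joints. The raters are also those who give the PASDAS globals, so the selection can favour pairs whose errors agree, as step 5 of the working shows.

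Any bias from true change is also conservative, and the ICC feeds no treatment comparison.

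**Conclusion.** The point holds in a conditional form. The analysis uses all available screening-baseline pairs without checking stability, and ICC(1,1) counts true change as error. The coefficient therefore estimates reliability plus any true change over an interval of up to four weeks.

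With an assumed error-only ICC of 0.85 and S = 1.57 under model (A), the expected value is about 0.83, 0.81 or 0.77 for a true-change SD of 0.3, 0.5 or 0.7. The last is a fall of 0.077, about 40% of the planned interval width of 0.2. Larger falls need larger assumed change, a smaller assumed baseline SD, or model (B). Carried-forward baselines, if they entered the pairs, would act in the opposite direction.

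The consequence is confined to one secondary objective. The primary treatment comparison and the sample size of 84 do not depend on this ICC. The change is worth making because a low value could not otherwise be interpreted and the data for a check are already collected.

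**What to change.** In SAP 11.3:

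- Keep the ICC in all patients with both scores as the main estimate, and describe it as reliability plus any true change over the interval.
- Add a supplementary ICC(1,1), with its 95% interval, in patients whose patient and physician articular Likert ratings are both unchanged from screening to baseline.
- Report the distribution of the interval between the two visits, and the mean PASDAS difference with its SD.
- Exclude from both ICCs any pair whose baseline value was carried forward from screening under SAP 8.2.
- Interpret the two ICCs together, stating that the first may be too low if disease changed and the second somewhat too high because of how patients were selected.

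The cost is one extra analysis and a few descriptive figures, with no new data. The subset interval will be wider, and will exceed the planned 0.2 if fewer than 31 patients qualify. SAP version 4.0 postdates unblinding, so the addition should be labelled unplanned, as SAP 2 and 5.2 already allow. It uses only pre-treatment data and no treatment allocation.
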